8.0 Dosage Modifications/Toxicity

8.1 Toxicity

Toxicities and Adverse Events will be assessed during each monthly clinic visit using the NCI CTCAEversion 4.03. Since CTEP has standardized the CTC, the NCI does not require the inclusion of the CTCAE within this protocol document. However, all appropriate treatment areas will have access to a copy of the CTCAEversion 4.03. A copy can be downloaded from the CTEP home page: http://ctep.cancer.gov

Dose re-escalation after prior dose reduction due to toxicity will not be permitted.

8.2 Dose Modifications for Specific Toxicities

8.2.1 Management of Hypokalemia

Every patient that experiences Grade 1 hypokalemia (serum potassium < 3.5 mM or below lower limit of normal range, but \ge 3.0 mM) will require oral potassium supplementation, and will be monitored bi-weekly until serum potassium is between 3.5 to 5.0 for \ge 4 weeks. The frequency of testing after supplementation is at Investigator discretion. The dose of potassium supplement must be titrated to maintain serum potassium at \ge 3.5mM but \le 5.0 mM. If any patient experiences Grade 3 hypokalemia (serum potassium levels < 3.0 mM but \ge 2.5 mM) study treatment will be held, and the patient will be given intravenous and/or oral potassium replacement. If hypokalemia resolves and potassium level remains > 3.5 mM on a stable oral dose for a period > 1 week, itraconazole may be restarted at 200 mg/day per discretion of study investigator. If hypokalemia recurs to grade 3 or higher, itraconazole will be permanently discontinued and the patient will be hospitalized for IV potassium supplementation and cardiac monitoring. Any treatment delay greater than 4 weeks will result in permanent discontinuation of the study drug.

	Grade of		
Serum Potassium	Hypokalemia	Action	Further Action/Maintenance
< 3.8 mM – 3.0 mM	1/2	Initiate oral K+ supplementation and increase frequency of K+ lab monitoring to bi-weekly	Titrate oral K+ dose to maintain concentration $3.5 - 5.0$ mM
< 3.0 – 2.5 mM	3	Hold itraconazole; initiatestanding oral supplementation +/- temporary IV supplementation	If K+ > 3.5 mM for > 1 week, re- initiate itraconazole at 200 mg/day per investigator discretion
< 2.5 mM	4	Permanently discontinue itraconazole; hospitalize for IV supplementation and cardiac monitoring	Permanently discontinue itraconazole

8.2.2 Management of Elevated Liver Function Tests

If Grade 1 increases in AST, ALT, or total bilirubin occur (AST or ALT > ULN – 3.0 x ULN or bilirubin > ULN – 1.5 x ULN), the frequency of LFT monitoring will be increased to bi-weekly but dose reduction and/or delay will not be mandated. If Grade 2 increases in AST, ALT or total bilirubin occur (AST or ALT > $3.0 - 5.0 \times$ ULN or bilirubin > $1.5 - 3.0 \times$ ULN, itraconazole will be held until the LFT abnormality improves to Grade 1 or lower, at which point the study drug will be restarted at 400 mg/day. If a grade 2 increase in AST, ALT, or bilirubin recurs, itraconazole will be held until improved to Grade 1 or lower in severity, and then restarted at 200 mg/day. If Grade 3 increases in AST, ALT, or bilirubin occur (AST or ALT > $5.0 - 20.0 \times$ ULN or bilirubin > $3.0 - 10.0 \times$ ULN, itraconazole will be held until the LFT abnormality improves to Grade 1 or lower (AST or ALT > $5.0 - 20.0 \times$ ULN or bilirubin > $3.0 - 10.0 \times$ ULN, itraconazole will be held until the LFT abnormality improves to Grade 1 or lower, at which point study drug may be restarted at 200 mg/day per individual investigator discretion. If a grade 3 increase in AST, ALT, or bilirubin recurs, itraconazole will be permanently discontinued. If a grade 4 increase in AST, ALT, or bilirubin occurs, itraconazole will be permanently discontinued. Any treatment delay greater than 4 weeks will result in permanent discontinuation of itraconazole.

AST or ALT	Grade of LFT		Further
Bilirubin	Abnormality	Action	Action/Maintenance
>ULN - 3X ULN > ULN - 1.5 X ULN	1	Increase frequency of LFT monitoring to bi-weekly	None
> 3.0 – 5.0 X ULN > 1.5 – 3.0 X ULN	2	Hold itraconazole; increase frequency of LFT monitoring to weekly	If improves to Grade 1 or lower, re-initiate at 400 mg/day. If recurrent grade 2 AE, hold until Grade 1 or lower, then re-start at 200 mg/day.
> 5.0 – 20.0 X ULN > 3.0 – 10.0 X ULN	3	Hold itraconazole; increase frequency of LFT monitoring to weekly	If improves to Grade 1 or lower, re-initiate at 200 mg/day per investigator discretion. If recurrent grade 3 AE, perman- ently discontinue itraconazole.
> 20.0 X ULN > 10.0 X ULN	4	Permanently discontinue itraconazole	N/A

8.3 Dose Modification for Other Adverse Events

For adverse events of grade 1 in severity, treatment will be per institutional guidelines, and no dose interruption will be mandated. For adverse events of grade 2 in severity that the study investigator deems as possibly, probably or definitely related to study drug, treatment will be interrupted until the adverse event resolves to grade ≤ 1 in severity, at which point itraconazole will be re-started at a reduced dose of 400 mg/day. If a patient experiences a recurrent adverse event of grade 2 in severity, itraconazole will be held until the adverse event resolves to grade ≤ 1 in severity, at which point itraconazole will be held until the adverse event resolves to grade ≤ 1 in severity, at which point itraconazole will be held until the adverse event resolves to grade ≤ 1 in severity, at which point itraconazole will be re-started at 200 mg/day.

Treatment will be interrupted for grade 3 adverse events that study investigator attributed as possibly, probably, or definitely related to study medication. Treatment will be held until the adverse event resolves to grade ≤ 1 in severity, at which point therapy will be re-instituted at a reduced dose of 200 mg/day. If the adverse event recurs to grade 2 in severity, treatment will be held until the adverse event resolves to grade ≤ 1 in severity, at which point therapy will be re-instituted at 200 mg/day per individual investigator discretion. If the adverse event recurs to grade 3 or higher in severity, treatment will be permanently discontinued and patients will not be re-challenged for any grade 4 adverse events occurring while receiving protocol therapy.

Grade of Other AE	Action	Further Action/Maintenance
1	Treatment per institutional guidelinesNo dose interruption will be mandated	None
2	 Treatment interrupted until the adverse event resolves to grade ≤ 1 in severity @ ≤ 1 in severity, re-start itraconazole at reduced dose of 400 mg/day 	 If recurrent grade 2 AE, hold itraconazole until resolves to grade ≤ 1 in severity @ ≤ 1 in severity, re-start itraconazole at reduced dose of 400 mg/day
3	 Treatment interrupted and held until resolves to grade ≤ 1 in severity @ ≤ 1 in severity, re-start itraconazole at reduced dose of 200 mg/day 	 If recurrent grade 2 AE, hold itraconazole until resolves to grade ≤ 1 in severity @ ≤ 1 in severity, re-start itraconazole at reduced dose of 200 mg/day If the AE recurs to grade 3 or higher in severity, permanently discontinue treatment

If there is a greater than 4 week delay in treatment, protocol therapy will be permanently discontinued.

Grade of Other AE	Action	Further Action/Maintenance
4	Treatment permanently discontinued and patients will not be re-challenged	N/A

Dose re-escalation after prior dose reduction due to toxicity will not be permitted.

9.0 Laboratory Assessment and Correlative Studies

9.1 Serum Hormone Levels

Serum hormone levels will be measured at baseline, week 4, week 12, and at the time of PSA or clinical progression for patients enrolled onto this study.Serum hormone levels should be drawn between 8:00 am and 12:00pm, please see table below for all collection parameters.Peripheral blood for serum hormone levels will be processed and stored using procedures outlined below and in appendix 3 section IV.The blood will be shipped to UCSF (see appendix 3 section IV) and subsequently analyzed at UCSFaccording to the methods outlined below.

	Time of				
	Day	Method	Volume	Container	Processing
Testosterone	Any	LC/MS/MS	2 mL	Red Top	Separate serum and freeze at -20 degrees C
Androstenedione	AM*	LC/MS/MS	2 mL	Red Top	Separate serum and freeze at -20 degrees C
DHEA-S	Any	RIA after hydrolysis	1 mL	Gold Top	Separate serum and freeze at -20 degrees C
АСТН	AM	CLIA	3 mL	Lavender Top (pre-chilled); deliver on ice to laboratory	Separate serum and freeze plasma in plastic tube at -20 degrees C
Cortisol	AM	CLIA	1 mL	Gold Top	Separate serum and freeze at -20 degrees C
Aldosterone	AM	LC/MS/MS	2 mL	Red Top	Separate serum and freeze at -20 degrees C
11-Deoxycortisol	AM	RIA	2 mL	Gold Top	Separate serum and freeze at -20 degrees C

	Time of				
	Day	Method	Volume	Container	Processing
Deoxycorticosterone	AM	RIA	2 mL	Gold Top	Separate serum and freeze at -20 degrees C

* Between 8:00 am and 12:00pm* Between 8:00 am and 12:00pm

DHEA-S = dihydroepiandrostenedione-sulfate; LC = liquid chromatography; MS = mass spectroscopy; RIA = radioimmunoassay; CLIA = chemiluminescent immunoassay

9.2 Hedgehog Pathway Assessment BymRNA Expression Analysis

Because Hedgehog signaling is present in skin and hair follicles, *GL11* mRNA expression (a marker of Hedgehog pathway activation) will be analyzed using 3-millimeter skin punchbiopsies from hair-containing non-scalp skin (e.g. upper back or arms) obtained at baseline and after 4 weeks on study, using previously described and validated methodology [25]. The skin sample should be placed immediately into a 5 mL Tissue Protect Tube containing RNAlater solution, and care must be taken to ensure that the skin sample is fully submerged in RNAlater. Samples should then be frozen at -20 degrees Celsius or colder until the time of RNA extraction. Additionally, mRNA expression analysis of archived, formalin-fixed paraffin embedded primary prostate cancer tissue will be performed when tissue is available. Please see Appendix 3 for details regarding the skin biopsy procedure as well as specimen handling/shipping instructions.

*GLI1*mRNA expression levels in tissue samples will be analyzed using the RT² Profiler Custom PCR Array protocol (SABiosciences, Qiagen). RNA will be extracted from tissue samples using RNeasy Fibrous Tissue kit (Qiagen). The RT² PCR Array First Strand kit (SuperArray Bioscience), will be used to synthesize cDNA. Quantitative PCR will be performed using RT² Real-Time SYBR Green PCR Master Mix (SABiosciences, Qiagen), in an ICycler PCR System (Bio-Rad Laboratories), according to the manufacturer's protocol. The housekeeper gene *GAPDH* will be used, as the expression level of this gene has been previously shown to not change with itraconazole therapy using a housekeeper array (Cat#: PHAS-000, SABiosciences, Qiagen). Cycling threshold (C_t) values for *GLI1*and *GAPDH* from each experiment will be analyzed using the SABiosciences software and fold change of *GLI1*expression, normalized to *GAPDH*, will be derived for each sample.

Patients will be dichotomized for the purposes of statistical analysis. The full statistical analytic plan for *GLI1* expression datais described in Section 10.

9.4 Serum Drug Levels

The plasma trough concentrations of itraconazole and hydroxyitraconazole will be assessed by a validated liquid chromatography-mass spectrometry assay developed by the Analytical Pharmacology Core Laboratory at Johns Hopkins University. Trough levels will be drawn after 4 weeks of protocol therapy, collected before the morning dose of itraconazole. Patients should hold their morning dose until the collection is completed.

Patients will have about 5 ml of blood collected into tubes containing K2-EDTA as an anticoagulant (lavender top). Following extraction, blood will be immediately placed on ice or refrigerated until processed. The actual day and time of collection will be recorded. Plasma will be separated from whole blood as soon as possible following extraction. This will be done by centrifuging whole blood at 1000 x g for 10 minutes at 4°C. Plasma will then be transferred to a screw-cap polypropylene cryotube for determination of itraconazole and hydroxyitraconazole concentrations. The polypropylene tube will be labeled with patient''s initials, study number, day, time, and protocol day and then frozen at -70° C until the time of analysis (see appendix 3 for additional information regarding processing and shipping instructions).

10.0 Planned Statistical Methods

10.1 Study Design

This is a phase II, single arm study of itraconazole dosed at 300 mg BID in patients with noncastrate, non-metastatic, biochemically relapsed prostate cancer after prior definitive local therapy. Simon's two stage minimax design will be followed for accrual and include an interim test for lack of efficacy (see Sections 10.2 and 10.4). There is a pre-specified stopping rule for

safety after 10 patients have been treated for a minimum of 8 weeks of protocol therapy (see Section 10.4). Patients will remain on protocol therapy until the first occurrence of any of the following: PSA progression, as defined in Section 2, development of metastasis, unacceptable toxicity, initiation of non-protocol therapy, or patient/physician withdrawal from study. Patients will remain on study until development of metastasis, initiation of non-protocol therapy, or patient/physician withdrawal from study, whichever occurs soonest. The total study duration including follow up is expected to be 3 years from the date of first patient enrolled onto study.

10.2 Determination of Sample Size and Study Power

This is a single arm phase II study to test the hypothesis for an improvement in the proportion of patients achieving a PSA decline of at least 50% from baseline with itraconazole therapy. The null hypothesis is that 10% of patients treated with itraconazole will achieve a > 50% decline in serum PSA after 12 weeks of protocol therapy. This response proportion is based upon the overall PSA response proportions observed in prior clinical trials of non-castrating agents in biochemically relapsed prostate cancer, which demonstrated modest activity with 0-10% of patients achieving a \geq 50% PSA decline on therapy [10-16]. A response proportion of 10% or less in the current study would indicate minimal disease activity and would not justify further testing of itraconazole in this disease setting. The alternative hypothesis is that 25% of patients treated with itraconazole will achieve a > 50% decline in serum PSA after 12 weeks of protocol therapy, a clinically meaningful result that would represent promising biologic activity of a novel potentially non-castrating agent tested in the biochemically relapsed disease setting. The sample size is based upon the primary study endpoint and will follow a two stage design for accrual following Simon"s two-stage minimax approach. Twenty-two patients will be accrued at the first stage. If more than two patients achieve a PSA decline of at least 50% within 12 weeks of starting protocol therapy, accrual will continue to the second stage and an additional 18 patients will be entered. If at least 8 of the 40 patients entered on study achieve a PSA decline of at least 50%, then the null hypothesis will be rejected in favor of the alternative. This test with a total evaluable accrual of 40 patients has a power of 80% and a directional level of significance of 0.05. The probability of stopping accrual at the first stage is 0.62 if the null hypothesis is true. A drop-out rate for reasons not due to treatment or disease progression of 5% prior to the cut-off point for the primary analysis is assumed for a total study accrual of 42 patients.

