10.3 Accrual

A total of 40 evaluable patients will be enrolled across three investigational sites. The estimated enrollment rate across the three sites is 3 patients per month, leading to anticipated enrollment duration of approximately 14 months. The duration from first patient enrolled to primary analysis is approximately 18 months, and the total study duration including follow upis expected to be 3 years.

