10.4 Interim Analysis

There will be an interim analysis for safetyafter 10 patients have received a minimum of 8 weeks of protocol therapy. Study accrual will continue during the interim safety analysis.

If, after 8 weeks of protocol therapy, four or more out of ten patients have a grade 3 or higher adverse event that the study investigator deems as possibly, probably, or definitely related to study drug (excluding hypokalemia or hypertension), the study will close to further accrual.

An interim analysis for lack of efficacy will be performed after completion of the first stage of accrual of 22 patients. Study accrual will not stop for this analysis, consistent with the study design of prior non-hormonal therapies in biochemically relapsed prostate cancer, the majority of which were single stage phase II studies without pre-specified stopping rules for lack of efficacy despite observed PSA response proportions of less than 5%.

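### The 0.62 in section 10.2 is the chance that the futility rule is met, not the chance that accrual stops at 22 men, because accrual stays open through the look

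*Combined protocol and SAP*

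**What the plan says.** Section 10.2 sets the hypotheses: "The null hypothesis is that 10% of patients treated with itraconazole will achieve a > 50% decline in serum PSA" and "The alternative hypothesis is that 25% of patients treated with itraconazole will achieve a > 50% decline in serum PSA", both after 12 weeks. The sample size "will follow a two stage design for accrual following Simon's two-stage minimax approach". On the first stage it says "Twenty-two patients will be accrued at the first stage". If more than two of them respond, "accrual will continue to the second stage and an additional 18 patients will be entered". The null is rejected with at least 8 responders of 40. The section then states: "The probability of stopping accrual at the first stage is 0.62 if the null hypothesis is true". Total accrual is set at 42 to allow for 5% drop-out.

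Section 10.4 places the lack-of-efficacy look after the 22 first-stage men are accrued and adds: "Study accrual will not stop for this analysis". Section 5.2.1 likewise says that accrual continues during both planned looks, but it puts the efficacy look after 30 men have been treated for at least 12 weeks.

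Section 10.3 gives the pace: "The estimated enrollment rate across the three sites is 3 patients per month". Sections 10.7.1 and 10.8.1 require a response after 12 weeks to be confirmed by a repeat PSA at least 2 weeks later.

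**The concern.** Section 10.2 reads as a sequential design: enrol 22, look, and enter 18 more only if the drug passes. On that reading an inactive drug has a 62% chance of being given to 22 men and no more. If enrolment runs on while the 22nd man completes 12 weeks, accrual cannot stop at 22, and the sentence describes a property that the trial does not have. At stake is the number of men exposed to an inactive drug, which anyone approving or citing the design would take from section 10.2. The two different first-look sizes (22 and 30) make it harder still to know what the 0.62 refers to.

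**Working it through.** **Inputs.** Null rate 0.10, alternative 0.25, first stage 22 men with continuation if more than 2 respond, total 40 with rejection at 8 or more, accrual cap 42 (all 10.2); 3 men a month (10.3); accrual not paused (10.4, 5.2.1); confirmation at least 2 weeks after week 12 (10.7.1, 10.8.1). Assumed: uniform accrual, no data-processing lag, 4.348 weeks per month.

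**1. Reproduce the plan's figure.** P(X ≤ 2 | n = 22, p = 0.10) = 0.9^22 + 22(0.1)(0.9^21) + 231(0.01)(0.9^20) = 0.0985 + 0.2407 + 0.2808 = 0.620. The stated 0.62 is right as the probability that the futility rule is met. A grid search also returns 2/22, 7/40 as the minimax design for these hypotheses at 5% and 80%.

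**2. Enrolment when stage 1 can be read.** The 22nd man enters at 22/3 = month 7.3. Enrolled at read-out = 22 + 3 × (weeks/4.348):

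| Read-out | Month | Enrolled |
|---|---|---|
| Week 12, no confirmation needed | 10.1 | 22 + 8.3 = 30.3 |
| Week 14, confirmation awaited | 10.6 | 22 + 9.7 = 31.7 |

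If 22 evaluable men require 22/0.95 = 23.2 enrolled, the figures are 31.4 and 32.8. If confirmation waits for the next monthly PSA (6.3.5), week 16 gives 33.0. For an assumed 2 to 4 men a month, the range is 27.5-33.0 at week 12 and 28.4-34.9 at week 14.

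**3. Expected enrolment under the null**, using the same cap on both sides:

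| | Paused at 22 | Not paused, week 12 | Not paused, week 14 |
|---|---|---|---|
| Cap 40 | 22 + 0.38 × 18 = 28.8 | 0.62 × 30.3 + 0.38 × 40 = 34.0 | 0.62 × 31.7 + 0.38 × 40 = 34.9 |
| Cap 42 | 22 + 0.38 × 20 = 29.6 | 0.62 × 30.3 + 0.38 × 42 = 34.7 | 0.62 × 31.7 + 0.38 × 42 = 35.6 |

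When the rule is met, the second-stage men spared number 40 − 31.7 = 8.3 to 40 − 30.3 = 9.7, against 18 in the paused design.

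**4. Effect on the test.** Exact binomial, summed over stage-1 outcomes:

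| | Type I error | Power |
|---|---|---|
| Stop at ≤ 2/22 binding | 0.040 | 0.803 |
| Look ignored, reject at ≥ 8/40 | 0.042 | 0.818 |

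**5. The 30-man timing in 5.2.1.** Enrolled at read-out is 30 + 8.3 = 38.3 (week 12) or 30 + 9.7 = 39.7 (week 14), so almost no accrual is left to stop. Section 5.2.1 gives no boundary. If the 10.2 boundary were carried over, P(X ≤ 2 | n = 30, p = 0.10) = 0.0424 + 0.1413 + 0.2277 = 0.41, not 0.62.

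**The case against.** The strongest reply is that nothing is miscalculated or hidden. 0.62 is the usual early-termination probability for this design. Sections 10.4 and 5.2.1 say openly that accrual continues and give reasons: the drug's safety record, continuous monitoring, a largely asymptomatic population, and earlier single-stage trials in this setting. All of that stands. It justifies not pausing, but it does not make the sentence in 10.2 true, and neither section restates the enrolment consequences.

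A second reply is that waiting for confirmation overstates the delay. A man without a 50% decline at week 12 needs no repeat PSA, men who stop before week 12 already count as failures (10.8.1), and the stage-1 rule in 10.2 mentions no confirmation. This also stands. Futility will usually be readable at about 30 men; 32 applies when unconfirmed responses could still bring the count to three.

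A reader might infer that the look is worthless, or that it saves almost nothing if accrual is faster. The documents do not support this for a look at 22: at the only documented rate, a failed look still prevents about 8-10 enrolments. A reader might also infer that 10.8.1 lets men enrolled after the 22nd rescue a failed first stage. That section opens by applying the two-stage rules of 10.2, so it does not grant this. But 10.2 states only the condition for continuing, and 10.4 spells out closure for the safety look but no action for the efficacy look. The status of the extra men therefore still needs a sentence.

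**Conclusion.** The point holds as a mislabelled operating characteristic. The 0.62 is the correct probability that the futility rule is met, but the chance of accrual stopping at 22 is effectively nil when enrolment is not paused. Under the null, expected enrolment is about 34-35 against 28.8 (40-man cap), or about 35-36 against 29.6 (42-man cap). That rests on 3 men a month, uniform accrual and no processing lag.

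The tempting stronger readings, that 0.62 is an arithmetic error or that the continuing accrual inflates the type I error, are not supported. The figure reproduces exactly, and the error rate stays below 0.05 whether the stop is binding or ignored. The separate conflict between 22 men (10.2, 10.4) and 30 men (5.2.1) is real. It matters because the later timing would remove nearly all of the remaining saving.

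**What to change.** - In 10.2, restate 0.62 as the probability under the null that the futility rule is met on the first 22 evaluable men. Add that, because accrual is not paused, about 30-32 men are expected to be enrolled at read-out and expected enrolment under the null is about 34-35 (40-man cap).
- State that the stage-1 decision uses the first 22 evaluable men only, that men enrolled later cannot reverse it, and that their results are then reported descriptively.
- Reconcile the timing of the efficacy look in 5.2.1 with 10.2 and 10.4.

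The cost is protocol wording only; the sample size and the boundaries in 10.2 do not change. The downside is that the stated operating characteristics become less favourable.
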